### **6.0      STUDY TREATMENT AND SUPPLIES**

The identity and instructions for administration, storage, and handling of HEPLISAV-B are described below.

## **6.1 Study Treatments**

The investigational vaccine to be tested is HEPLISAV-B, a licensed, commercially-available hepatitis B vaccine consisting of 20 mcg of HBsAg and 3000 mcg of cytidine phosphoguanosine (CpG) 1018 adjuvant.

HEPLISAV-B [Hepatitis B Vaccine (Recombinant), Adjuvanted] is a sterile solution for intramuscular injection. Each 0.5 mL dose contains HEPLISAV-B in a solution for injection supplied as a single-dose. Additional information for HEPLISAV-B is provided in the USPI ([Appendix 2](#)).

## **6.2 Instructions for Administration**

Administer HEPLISAV-B by intramuscular injection in the deltoid muscle region using the pre-filled syringe. HEPLISAV-B administration must be performed prior to the start of dialysis on study visit days.

## **6.3 Labeling**

During the course of the study, HEPLISAV-B labeled for clinical study use will be provided.

At a minimum, HEPLISAV-B will be labeled with the following information: product name, product lot number, contents, volume, concentration, sponsor name, and a statement indicating that the drug is for investigational use only.

## **6.4 Storage and Handling Instructions**

HEPLISAV-B must be stored in a refrigerator at 2°C to 8°C (35°F to 46°F). Do not freeze. If frozen, continue to store the vaccine in the refrigerator but isolate it from other study vaccine and follow the temperature excursion procedures outlined in the Pharmacy Manual. Do not use the vaccine after the expiration date shown on the product label.

The clinical supplies storage area at the site must be monitored closely by the designated site staff for temperature consistency and documentation of temperature monitoring must be maintained. Temperature excursions outside of the recommended storage range may impact product quality and must be reported to Dynavax or its designee per the detailed instructions in the Pharmacy Manual.

## **6.5 Control and Accountability of Investigational Medicinal Product**

All investigational medicinal product must be received by a trained designated person at the study site, handled and stored safely and properly, and kept in a secured location with limited access.

The investigator (or responsible designee) must maintain current and accurate records of the receipt (documentation from shipments of study treatments received), administration (patient-by-patient and overall accounting) and return of study treatments to a Dynavax-specified facility for destruction. All study treatments must be stored in a location with access restricted to authorized personnel only.

A study monitor will be responsible for monitoring the drug accountability at the site. The monitor should be contacted with any questions concerning administration of study treatments.

Records of study treatments accountability, storage, and handling must be made available to the study monitor for the purposes of study treatments accountability. Any discrepancy and/or deficiency must be recorded with an explanation.

The investigator must retain all used product and expired, damaged, and unused study treatments until accountability has been confirmed by the study monitor. Any exceptions to this policy must be specifically permitted by Dynavax.

At the end of the study, or upon request by Dynavax, all unused study treatments must be returned to a Dynavax-specified facility for adequate disposition.

Refer to the Pharmacy Manual for detailed instructions on study treatments.

Study treatments may not be used for any purpose other than that described in the protocol.

## **6.6 Treatment Compliance**

All study injections will be administered by designated personnel only.

## **7.0 TREATMENT OF SUBJECTS**

### **7.1 Treatments Administered and Treatment Period**

Subjects will receive HEPLISAV-B administered intramuscularly in the deltoid muscle at Week 0 (Visit 1), Week 4 (Visit 2), Week 8 (Visit 3), and Week 16 (Visit 4) as outlined in the Schedule of Assessments ([Appendix 1](#)). HEPLISAV-B must be administered prior to the start of dialysis on each vaccine administration day.

## 7.2 Prohibited Treatments or Therapies

The following non-study medications are prohibited:

**14 days prior to Injection 1 and through 28 days following each injection:**

- any inactivated virus vaccine

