## **5.2 Exclusion Criteria**

A subject with any one of the following criteria is not eligible for the study:

- 1) Previous receipt of any hepatitis B vaccine
- 2) History of human immunodeficiency virus (HIV) or hepatitis C virus (HCV) infection or antibody to HIV or HCV
- 3) History of sensitivity to any component of HEPLISAV-B vaccine
- 4) Substance or alcohol abuse that in the opinion of the investigator would interfere with compliance or with interpretation of the study results
- 5) Recent or ongoing history of febrile illness (within 7 days of the first study injection)
- 6) Has received any of the following prior to the first study injection:
  - a) **Within 14 days:**
    - i) Any inactivated vaccine
  - b) **Within 28 days:**
    - i) Systemic corticosteroids (more than 3 consecutive days) or other immunomodulatory or immune suppressive medication with the exception of inhaled steroids
    - ii) Any live virus vaccine
    - iii) Granulocyte colony-stimulating factor (G-CSF) or granulocyte-macrophage colony-stimulating factor (GM-CSF)
    - iv) Any other investigational medicinal agent
  - c) **Within 90 days:**
    - i) Blood products or immunoglobulin
- 7) If female and pregnant, nursing, or planning to become pregnant during the study
- 8) Undergoing chemotherapy or expected to receive chemotherapy during the study period

9) Has a medical condition considered by the investigator likely to interfere with the subject's compliance or the interpretation of study assessments, including the following laboratory abnormalities which the investigator may consider if severe:

- a) Anemia
- b) Thrombocytopenia
- c) Leukocytosis
- d) Neutropenia
- e) Metabolic acidosis
- f) Increased alanine aminotransferase or aspartate aminotransferase
- g) Hyperkalemia
- h) Hypokalemia

10) Is scheduled to undergo a kidney transplant within 6 months of the first study injection

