#### **9.4.6 Post-injection Reaction Assessments**

Assessments of post-injection reactions will be collected for a minimum of 30 minutes following each of the HEPLISAV-B injections at the clinical site and as reported by the subject in a diary for 7 days. Information about the presence and severity of post-injection local (injection site) reactions (redness, swelling, and pain at or near the injection site) and systemic reactions (malaise, headache, myalgia, and fatigue) that are listed in the subject diary are considered solicited post-injection reactions. Oral temperature is also collected. Solicited post-injection reactions are related to treatment and recorded for 7 days following each study injection, including the day of injection. Post-injection reactions documented by the subject will be collected, reviewed by the study nurse/coordinator with the subject, and recorded on the appropriate eCRF. The grading criteria for post-injection reactions are in [Appendix 3](#). Further information is provided in the Study Reference Manual.

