# **10.0 REPORTING AND DOCUMENTATION OF MEDICALLY-ATTENDED ADVERSE EVENTS**

## **10.1 Post-Injection Reactions**

Local and systemic post-injection reactions are to be recorded on the subject diary. If they persist longer than 7 days (ie, 8 days or longer) and are medically attended (ie, subject seeks medical attention), they should also be recorded and reported as MAEs, per protocol Section [10.2](#). The severity of the post-injection reactions will be graded using the Toxicity Grading Scale for Healthy Adult and Adolescent Volunteers Enrolled in Preventive Vaccine Clinical Trials ([Appendix 3](#)).

Certain local and systemic events are routinely monitored in vaccine clinical trials as indicators of vaccine reactogenicity. It is recognized that each of these events, and particularly those of systemic nature, may under certain circumstances, in an individual subject, have a cause that is unrelated to study vaccine. However, as a matter of convenience and in accordance with common clinical practice, such events occurring within a specified period of time after immunization are herein termed ‘post-injection reactions’ and will be recorded as related to treatment.

Post-injection reactions documented by the subject via a diary will be collected, reviewed by the study nurse/coordinator with the subject, and recorded on the appropriate eCRF (Section [9.4.6](#)).

Further information is provided in the Study Reference Manual.

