9.2 Protocol Deviations

For the purpose of selecting subjects for the per-protocol population, a major protocol deviation is defined as one of the following:

- not meeting one or more enrollment criteria,
- anti-HBs serum sample obtained outside protocol specified visit window 4 weeks following the fourth study injection (Week 20 ± 7 days)
- 28 days prior to Injection 1 and through Week 20: received prohibited concomitant medications comprising systemic corticosteroids, other immunomodulators or immune suppressive medications (with the exception of inhaled steroids), immunoglobulin, DNA plasmids or oligonucleotides, or any other investigational medication.

A listing of patients with major protocol deviations will be provided describing their deviations. Any exclusions from analysis populations due to protocol deviations and other reasons will also be listed.

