9.7 Safety Analyses

Vaccine exposure and compliance will be summarized descriptively for safety population.

Safety data will be analyzed descriptively and will be based on the safety population. The most important safety parameters will be presented for all sites combined. Summary statistics will be used to describe the incidence of all post-injection reactions and MAEs (including SAEs, deaths, AMIs, and AESIs; further details regarding safety reporting of AMIs and AESIs are provided in Protocol Section 9.4.7.2). The incidence and proportion of post-

injection reactions and MAEs will be summarized. MAEs will be coded using the MedDRA SOC and PT.

The incidence of AMIs and major adverse cardiovascular events will be analyzed in subjects initiating hemodialysis after enrollment in the study and in subjects undergoing hemodialysis at the time of enrollment in the study.

The treatment-emergent period is defined in [Section 7.1](#).

Local and systemic post-injection reactions are to be recorded on the subject diary. If they persist longer than 7 days (i.e., 8 days or longer) and are medically attended (i.e., subject seeks medical attention), they should also be recorded and reported as MAEs, per protocol Section 10.2. The severity of the post-injection reactions will be graded using the Toxicity Grading Scale for Healthy Adult and Adolescent Volunteers Enrolled in Preventive Vaccine Clinical Trials.

Local reactions include redness, swelling and pain, and systemic reactions include malaise (not feeling well), headache, myalgia (body aches) and fatigue (feeling tired).

Post-injection reactions reported from day 1 to day 7 will be summarized by maximal severity and by vaccine group. The severity of local reactions, including redness and swelling will be categorized as none, 1 to ≤ 10 mm, >10 mm to ≤ 25 mm, >25 to ≤ 50 mm, >50 to ≤ 100 mm and >100 mm (severe local reactions).

The severity of pain and systemic reactions including malaise, headache, myalgia and fatigue occurring up to 7 days after each vaccination will be categorized as none, mild (no interference with activity), moderate (some interference with activity), severe (significant, prevents daily activity).

Temperature will be categorized as $<38^{\circ}\text{C}$ (no fever), $38\text{-}38.4^{\circ}\text{C}$, $38.5\text{-}38.9^{\circ}\text{C}$, $39\text{-}40^{\circ}\text{C}$ and $>40^{\circ}\text{C}$.

Each local and systemic reaction will also be categorized as none vs. any.

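### Protocol 5.2 and 7.2 name different classes of non-study vaccine, and SAP 9.7 does not separate diary weeks that overlap another vaccination, so the reactogenicity tables can include another vaccine's reactions

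*Protocol*

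**What the plan says.** **Entry rule.** Exclusion criterion 6a in Protocol 5.2, repeated in the synopsis, bars "Any inactivated vaccine" within 14 days. Its lead-in, "Has received any of the following prior to the first study injection", ties it to Injection 1 alone.

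**On-study rule.** Protocol 7.2 sets the period "14 days prior to Injection 1 and through 28 days following each injection", and the item listed under it is "any inactivated virus vaccine". Live virus vaccines are barred separately, from 28 days before Injection 1 through Week 28. Section 7.3 and the concomitant-medication footnote to Appendix 1 expect that some non-study vaccines will be given, and have them recorded through Week 28.

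**Attribution.** Protocol 9.4.6 states: "Solicited post-injection reactions are related to treatment and recorded for 7 days following each study injection, including the day of injection". Section 10.1 accepts that a systemic event may have another cause, but says that such events "will be recorded as related to treatment". SAP 9.7 says: "Post-injection reactions reported from day 1 to day 7 will be summarized by maximal severity and by vaccine group". It has no rule for a diary week that overlaps another vaccination, and SAP 9.8 plans no further analyses.

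**Links to conduct and populations.** Protocol 8.1 requires study treatment to stop for prohibited medications. Sections 8.3 and 9.4.5 re-check eligibility before each injection, so far as the criteria are relevant. SAP 9.2 counts "not meeting one or more enrollment criteria" as a major deviation; its prohibited-medication item names no non-study vaccine.

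**The concern.** Two operative rules cover the same 14 days with different classes of vaccine, and only the narrower one clearly runs on after Injection 1. Nothing then keeps a non-viral inactivated vaccine out of a diary week. Malaise, headache, myalgia, fatigue or fever that it caused would be tabulated as a HEPLISAV-B reaction. A single-arm study has no comparator in which the same background would show.

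The differing wording also affects conduct. If a subject receives a non-viral inactivated vaccine between injections, 7.2 read literally does not make it a prohibited medication under 8.1. A site that carries 6a forward through the eligibility re-check could decide otherwise. The documents do not say which reading is meant.

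**Working it through.** The plan states no figure on this point, so there is none to reproduce. The check is a comparison of wording plus day counting.

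**1. Class of vaccine**

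| Period | Protocol 5.2 (6a) | Protocol 7.2 |
|---|---|---|
| 14 days before Injection 1 | all inactivated vaccines | inactivated virus vaccines only |
| 28 days after each injection | does not apply | inactivated virus vaccines only |
| Days before Injections 2 to 4 | does not apply | no period of its own |

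Before Injection 1 both rules can be obeyed together, because 5.2 is the stricter. After it, inactivated non-viral vaccines are not prohibited on any day. The diary weeks on the nominal schedule are Days 1–7, 29–35, 57–63 and 113–119, and all four are open to them.

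**2. Inactivated virus vaccines**

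Inputs: injections on Days 1, 29, 57 and 113; visit window 0 for Injection 1 and ±7 days for the others (Appendix 1); 28 barred days after each injection (7.2).

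Open days before the next injection = interval − 28 − 1, not below 0.

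| Between injections | Interval, nominal (with windows) | Last barred day, nominal | Open days, nominal (with windows) |
|---|---|---|---|
| 1 and 2 | 28 (21–35) | 29 | 0 (0–6) |
| 2 and 3 | 28 (14–42) | 57 | 0 (0–13) |
| 3 and 4 | 56 (42–70) | 85 | 27 (13–41) |

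The nominal gap is Days 86–112: 56 − 28 − 1 = 27 days. Inactivated virus vaccines are barred inside every diary week, since 7 days is less than 28. Their only route into a diary is a dose shortly before an injection, which on the nominal schedule means Injection 4. If shortly before means 2 days, 2 of the 27 open days matter; if it means 7 days, 7 of them do.

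**3. Size, as an illustration only**

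Let p be the true reaction rate per injection, f the share of subjects given another vaccine in or just before a diary week, and q the chance that this vaccine causes the reaction, independently of HEPLISAV-B. Then

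overstatement = f × q × (1 − p).

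For p, the package insert in Appendix 2 gives fatigue of 10.8% to 17.4% per HEPLISAV-B dose in Studies 1 and 2, which were not studies of hemodialysis patients. The documents give neither f nor q; the values below are assumptions.

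- Low: f = 5%, q = 10%, p = 17.4%: 0.05 × 0.10 × 0.826 = 0.4 percentage points, or 115 × 0.0041 = 0.5 subjects.
- Same f, higher q: f = 5%, q = 30%, p = 10.8%: 0.05 × 0.30 × 0.892 = 1.3 points, or 1.5 subjects.
- High: f = 20%, q = 30%, p = 10.8%: 0.20 × 0.30 × 0.892 = 5.4 points, or 6.2 subjects.

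The result is driven by f, and nothing in the documents supports a value as high as one subject in five per injection.

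**The case against.** The strongest reply is that this is a one-word slip with little at stake. Solicited reactions are neither primary nor secondary endpoints. Recording them as related is a declared convention, and 10.1 says openly that the cause may lie elsewhere. Non-study vaccines are recorded, and SAP 9.4 lists all recorded medications, so a reader could trace an overlap by hand. All of this stands and keeps the point minor. It does not remove the inconsistency, and tracing by hand does not give a rate free of overlap.

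A reader might also infer several stronger things that the documents do not support:

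- **That per-protocol status is ambiguous for a vaccine given before Injection 1.** It is not. SAP 9.2 applies the enrollment criteria, 6a is explicit, and the vaccine line in 7.2 plays no part.
- **That the wording mismatch causes the gap before Injection 4.** It does not. That gap comes from the lack of a pre-injection period in 7.2, which may be intended, and would remain if the two wordings were aligned.
- **That all 27 open days bear on the diary.** Only the last few before Injection 4 plausibly do.
- **That a reaction after Injection 4 could stop dosing and cost per-protocol membership.** No injections remain to be stopped by then.

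**Conclusion.** The point holds as a minor one. Protocol 5.2 and 7.2 contradict each other on the class of vaccine, and both are rules that sites must act on. As written, another vaccine's reactions can enter the descriptive reactogenicity tables by two routes: a non-viral inactivated vaccine in any diary week, or an inactivated virus vaccine in the days just before Injection 4 (or before Injections 2 and 3 if those visits run late).

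The effect is probably small. The 0.4 to 5.4 points worked out above show how it scales with assumed f and q and are not an estimate. The seroprotection, medically-attended event, serious event, myocardial infarction and special-interest endpoints are not directly affected.

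Whether a subject vaccinated between injections may continue also remains unclear. This rests on reading the eligibility re-check as not clearly reapplying 6a at later injections; the text does not say that it does.

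**What to change.** 1. **Protocol.** The sponsor reconciles criterion 6a in 5.2 with 7.2 so that both name the same class of vaccine, and states whether a pre-injection period is intended for Injections 2 to 4. Which class and which period are the sponsor's decisions. The text should also make clear how the answer carries into 8.1 and the pre-injection eligibility re-check.
2. **SAP 9.7.** Flag each injection for which a non-study vaccine is recorded from a stated number of days before it (7, for example) through day 7 after it. Present the solicited systemic reaction and fever tables with and without the flagged injections.

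The cost is one wording correction, one SAP sentence and one extra set of tables based on slightly fewer injections. No new data are needed: vaccines are already recorded from 28 days before Injection 1 (Protocol 7.3) through Week 28. The SAP change is useful even if the protocol wording can no longer alter conduct.

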**28 days prior to Injection 1 and through Week 28:**

- Systemic corticosteroids (more than 3 consecutive days) or other immunomodulators or immune suppressive medication, with the exception of inhaled steroids
- Any live virus vaccine
- Granulocyte colony-stimulating factor (G-CSF) or granulocyte-macrophage colony-stimulating factor (GM-CSF)

**28 days prior to Injection 1 and through Week 68 (unless approved by sponsor):**

- Any other investigational medicinal agent (may be allowed after Week 28 [Day 197] upon sponsor approval)

**90 days prior to Injection 1 and through Week 28:**

- Blood products or immunoglobulin

If a subject requires treatment that is prohibited, the investigator should contact the Dynavax medical monitor or designee to determine whether the subject should receive further study injections. If the subject is not eligible for subsequent study injections, **the subject will not be withdrawn from the study, but** will be followed for safety through End-of-Study (EOS) Visit.

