#### **5.1 Inclusion Criteria**

A patient must meet all of the following criteria to be eligible for enrollment (defined as receiving the first study treatment [ie, HEPLISAV-B injection]) in the study:

- 1) Male and female subjects at least 18 years of age
- 2) Laboratory confirmed negative serology result to hepatitis B virus (HBV) surface antigen (HBsAg), antibody to hepatitis B surface antigen (anti-HBs), and antibody to hepatitis B core antigen (anti-HBc) prior to first study injection
- 3) Must be clinically stable and in the opinion of the investigator able to comply with all study procedures
- 4) Must be able and willing to provide informed consent
- 5) Receiving hemodialysis or will initiate hemodialysis within 4 weeks of first study injection
- 6) Women of childbearing potential (WOCBP) must consistently use an acceptable method of contraception or confirm in writing she will abstain from sexual activity from the Screening visit through 4 weeks after the last dose of study injection. Acceptable birth control methods include but are not limited to oral contraceptive medication, an intrauterine device (IUD), an injectable contraceptive (such as medroxyprogesterone acetate or Depo-Provera®), a birth control patch, or a barrier method (such as condom or diaphragm with spermicide).

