## **8.0 MANAGEMENT OF STUDY TREATMENT TOXICITIES**

### **8.1 Reasons for Stopping a Subject From Receiving Additional Injections**

The investigator will discontinue study treatment and notify the sponsor if any of the following MAEs occur:

- Grade 4 post-injection reaction within 7 days after any study injection
- Clinically significant Grade 3 or higher systemic reaction (eg, angioedema, generalized urticaria) within 7 days after any study injection
- Grade 3 or 4 hypotension within 24 hours of any study injection
- Grade 3 or 4 respiratory reaction or symptoms occurring within 24 hours of any study injection
- Any life-threatening event, regardless of relationship to study drug
- Any AMI (further details regarding safety monitoring of AMIs are provided in Section [9.4.7.2](#))
- Any confirmed AESI (further details regarding safety monitoring of AESIs are provided in Section [9.4.7.2](#))

Subjects must also be discontinued from study treatment for any of the following reasons:

- Violation of protocol eligibility criteria
- Prohibited medications
- SAE assessed as a suspected adverse reaction (SAR) or adverse reaction (AR)
- Pregnancy or breastfeeding

Subjects may be discontinued from the study for any of the following reasons:

- Violation of protocol eligibility criteria (only if the subject has not received any study treatment)
- Prohibited medications (only if the subject has not received any study treatment)
- Noncompliance with study procedures as determined by the investigator or sponsor
- The discretion of the investigator

- The sponsor's administrative decision to terminate the study

The investigator or designee must notify Dynavax within 24 hours when a subject has been discontinued from treatment due to an MAE. The subject should not be withdrawn from the study and should continue to be followed for safety (as defined in Section 9.7) through EOS Visit.

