## **11.2 Study Analysis Populations**

The Safety Population will comprise all subjects who received at least 1 study injection, excluding subjects who have no on-study safety data.

The Per-protocol (PP) Population for the immunogenicity analysis will comprise all subjects who receive all study injections, have no major protocol violations (to be specified in the Statistical Analysis Plan), and have anti-HBs levels obtained within the study visit window at Week 20.

The modified intent-to-treat (mITT) population for the immunogenicity analysis will comprise all subjects who receive at least 1 study injection and have at least 1 post-injection immunogenicity evaluation.

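### Protocol 7.2 and 8.1 give different dosing rules after a prohibited medication, and SAP 9.2 leaves post-Injection 1 blood-product users in the per-protocol set

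*Protocol*

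**What the plan says.** **Dosing.** Protocol 7.2 opens its list with "The following non-study medications are prohibited". One entry, running from 90 days before Injection 1 through Week 28, is "Blood products or immunoglobulin". If such a treatment is needed, "the investigator should contact the Dynavax medical monitor or designee to determine whether the subject should receive further study injections". The next sentence covers only the subject who is found ineligible for more injections, so continuing is an allowed outcome. Protocol 8.1 states "Subjects must also be discontinued from study treatment for any of the following reasons", and the list that follows includes prohibited medications with no qualifier.

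**Per-protocol set.** Protocol 11.2 requires that PP subjects "have no major protocol violations (to be specified in the Statistical Analysis Plan"). SAP 6.3 requires all study injections, no major deviation under SAP 9.2, and an in-window Week 20 anti-HBs result. SAP 9.2 names three kinds of major deviation:

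- The first is "not meeting one or more enrollment criteria". Protocol 5.1 speaks of a patient being "eligible for enrollment (defined as receiving the first study treatment", so these criteria concern the state before Injection 1. They include exclusion 6c, which bars blood products or immunoglobulin in the preceding 90 days.
- The second is a Week 20 sample outside its window.
- The third runs from 28 days before Injection 1 through Week 20: "received prohibited concomitant medications comprising systemic corticosteroids, other immunomodulators or immune suppressive medications (with the exception of inhaled steroids), immunoglobulin", followed by DNA plasmids or oligonucleotides and other investigational medication. Blood products are not named.

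SAP 9.6 bases the immunogenicity analysis on the PP set.

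**The concern.** There are two separable points.

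1. A site facing a prohibited medication has two instructions. Contacting the monitor and then stopping satisfies both. Contacting the monitor and then dosing with approval follows 7.2 and breaks a mandatory rule in 8.1. Nothing ranks one section above the other.

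2. The protocol handles blood products and immunoglobulin as one item, both at entry and on study. The SAP keeps them together before Injection 1 and separates them afterwards. An exposure close to the primary-endpoint sample is then tolerated when a remote one is disqualifying. At stake is who counts in the PP Week 20 SPR.

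**Working it through.** **Step 1: the dosing rules side by side.**

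| Action after a prohibited medication | Protocol 7.2 | Protocol 8.1 |
|---|---|---|
| Monitor contacted, treatment stopped | consistent | consistent |
| Monitor contacted, injection approved and given | consistent | breach |

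Elsewhere 8.1 does add qualifiers. Only a confirmed adverse event of special interest stops treatment, which matches the hold-and-resume procedure in 9.4.7.1.1. In the study-withdrawal list of the same section, prohibited medications carry a limiting parenthesis. The treatment-stop entry has neither. Blood products come under both rules because 7.2 classes everything on its list as a prohibited medication.

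**Step 2: PP status by timing.** Inputs are exclusion 6c, the first and third bullets of SAP 9.2, SAP 6.3, and the nominal days in the schedule (Injection 4 on Day 113, Week 20 sample on Day 141). Assume no other deviation and an in-window sample.

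| Exposure | Immunoglobulin | Blood products |
|---|---|---|
| 80 days before Injection 1 | out (6c, first bullet) | out (6c, first bullet) |
| Between Injections 1 and 4 | out (third bullet) | out if injections stop; in if all four are given |
| 10 days before the Week 20 sample (141 − 10 = Day 131) | out (third bullet) | in |

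The middle row spans 113 − 1 = 112 nominal days. There, PP status for blood products follows the dosing decision, because PP needs all four injections. The last row falls in the final 141 − 113 = 28 days, when no dose is left to withhold and the 7.2/8.1 conflict has no bearing.

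**Step 3: the plan's own figures.** Clopper-Pearson limits are lower = Beta(0.025; x, n − x + 1) and upper = Beta(0.975; x + 1, n − x). With n = 100, x = 80, 86, 90 and 95 give lower limits of 70.8%, 77.6%, 82.4% and 88.7%, and widths of 0.165, 0.145, 0.127 and 0.096. SAP Table 5-1 is reproduced exactly and is not in dispute.

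**Step 4: possible size.** The documents give no frequency of blood-product use, so k = 1, 3 or 5 affected PP subjects is an assumption. Start from the table row 86/100 (86.0%, 95% CI 77.6% to 92.1%) and remove k subjects. If all k were responders, the SPR becomes (86 − k)/(100 − k). If none were, it becomes 86/(100 − k). The width column instead holds the SPR at 86%, using x = 0.86n.

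| k removed | All k responders | No k responders | Width at fixed 86% | Change from 0.1450 |
|---|---|---|---|---|
| 1 | 85/99 = 85.9% | 86/99 = 86.9% | 0.1458 | +0.0008 |
| 3 | 83/97 = 85.6% | 86/97 = 88.7% | 0.1474 | +0.0024 |
| 5 | 81/95 = 85.3% | 86/95 = 90.5% | 0.1490 | +0.0040 |

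The SPR columns are extremes. If removed subjects respond at the overall rate, the estimate hardly moves.

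**The case against.** **The SAP list may be deliberate.** Protocol 11.2 leaves major violations to the SAP, and SAP 9.2 is plainly not a copy of 7.2. It ends at Week 20 rather than Week 28, adds DNA plasmids or oligonucleotides, drops the three-day qualifier on corticosteroids and leaves out vaccines. Live and inactivated vaccines show the same before-and-after asymmetry. This stands. A reader might infer that blood products were left out by mistake, but the documents do not prove it. What remains is that the protocol pairs them with immunoglobulin, the SAP keeps only one of the pair, and no reason is given.

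**Section 7.2 may simply be the procedure for applying 8.1.** A site following 7.2 gets an individual ruling from the sponsor's side, and no safety harm is identified. That limits the consequence, but the mandatory wording in 8.1 still leaves no room for an approved injection.

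**The optional mITT analysis.** A reader might infer that the gap is worse because SAP 9.6 makes the mITT analysis optional. It is not. The mITT set has no prohibited-medication exclusion and would also keep these subjects.

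**The effect is small.** This also stands. SAP 9.2 and 9.4 provide listings of deviations, exclusions and medications from which such subjects could be traced, although a listing does not alter the reported estimate.

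**Conclusion.** Both points hold as matters of text, and no other section resolves either one. An injection approved under 7.2 contradicts 8.1. Blood products after Injection 1 are not a major deviation under SAP 9.2, so a subject exposed shortly before the Week 20 sample stays in the PP SPR.

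Severity is minor. The number of affected subjects is unknown and the effect is probably small. SAP 9.0 plans no hypothesis test, so no pass/fail result changes. A reader might infer that the SPR is biased. The documents support no direction, and the 90.5% extreme needs five affected subjects, all non-responders. The size figures rest on an assumed 1 to 5 affected subjects among 100 and a starting SPR of 86%.

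**What to change.** **1. Protocol, at the next amendment.** Make 7.2 and 8.1 state one rule. Either qualify the 8.1 entry so that prohibited medications stop treatment only when further injections are ruled out under 7.2, or turn 7.2 into a mandatory stop. The direction is the sponsor's choice. The edit is one bullet or one sentence, but Protocol 13.1 requires IRB approval of amendments and the synopsis lists 25 centers, so it should be bundled with other changes.

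**2. SAP 9.2, third bullet.** Replace immunoglobulin with *blood products or immunoglobulin*, keeping the Week 20 end point. The cost is two added words, the matching PP flag, and a check that the eCRF captures blood products; concomitant medications are already recorded through Week 28. PP status for blood products would then no longer depend on the dosing decision. If the omission was intended, one sentence of reasons in SAP 9.2 would explain it.

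**Timing.** SAP 8.0 and 9.9 allow an open-label look at the Week 20 SPR after about 50 subjects. The PP change should precede that look, so that it cannot appear driven by the data. Failing that, make it before the Week 20 database lock and document when it was made.

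**Downside.** A few subjects may leave PP, widening the interval by about 0.001, 0.002 or 0.004 if an assumed 1, 3 or 5 of 100 are lost. PP exclusions for vaccines are not requested.
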